## Protocol

#### Abstract

The overall goal is to determine whether differential activation in a priori regions of interest to select reward and inhibition probes can predict drug use during and following active treatment in patients addicted to cocaine, marijuana and prescription opiates. The active treatment is a behavioral intervention (Coping with Craving) for cocaine patients, baclofen for marijuana patients and naltrexone for prescription opiate patients. The treatment is directed toward improving the inhibition of cue- induced drug craving. Subjects must be physically healthy, treatment seeking men and women (ages 18-60), be able to read at eighth grade (or above) level, and voluntarily seeking treatment. Females must be non-pregnant, non-lactating and either be of non-childbearing potential or of child-bearing potential, but practicing a medically acceptable method of birth control. The main study interventions are functional magnetic resonance imaging and specific probes for reward and inhibition to determine whether the brain response to these probes can predict the primary clinical outcome of drug use/relapse, and secondary public health outcomes (e.g., unprotected sexual behavior leading to increased HIV risk) in an underserved population receiving state-of-the-art treatments for cocaine, marijuana and prescription opiate dependence.

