#### **Objectives**

#### **Overall objectives**

Objective 1: To determine whether differential activation in a priori brain regions of interest (ROI) to selected reward and inhibition probes can predict drug use during active treatment.

Hypothesis 1a: Greater activation of a priori limbic ROI (e.g., interconnected amygdala/ventral striatal cluster during brief drug cues; bilateral ventral striatum during reward risk) prior to (FMRI 1) and during (FMRI 2) active treatment will predict greater drug use during the active treatment phase.

Hypothesis 1b. Lower activation of a priori prefrontal inhibitory ROI (e.g., lateral orbitofrontal cortex; supragenual anterior cingulate) during affect-congruent Go-NoGo; inhibition of cue-triggered craving) prior to (FMRI 1) and during (FMRI 2) active treatment will predict greater drug use during the active treatment phase. Objective 2: To determine whether differential activation in a priori brain ROI to selected reward and inhibition probes can predict relapse following active treatment.

Hypothesis 2a: Greater activation of a priori limbic reward ROI (e.g., interconnected amygdala /ventral striatal cluster during brief drug cues; bilateral ventral striatum during reward risk during brief drug cues; reward risk) prior to (FMRI 1), and following (FMRI 3) active treatment will predict greater drug use during the 12-week follow-up period.

Hypothesis 2b: Lower activation of a priori prefrontal inhibitory ROI (e.g., lateral orbitofrontal cortex; supragenual anterior cingulate) during affect-congruent Go-NoGo; inhibition of cue-triggered craving) prior to (FMRI 1) and following (FMRI 3) active treatment will predict greater drug use during the 12 week follow- up period.

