Study Specific Background Prescription Opioids Prescription opioid abuse and dependence (POD) is illegal use of prescription opioids obtained on the black market for non-medical purposes. POD is a significant and growing public health problem [53, 54] both nationwide [55-57] and in Pennsylvania [23, 58]. Though the incidence of POD in the US is more than four times higher than heroin abuse and dependence [37], less is known about the clinical characteristics of POD than heroin dependence [59]. Relapse to drug use is a hallmark of opioid addiction. The harm of relapse in POD is compounded by the risk of transition to heroin [60]. The main clinical priorities in POD management are predicting vulnerability to relapse and predicting and monitoring patients' response to pharmacological treatment. Presently, both domains rely on history, physical examination and urine toxicology that are time-consuming and susceptible to subjective distortions [61, 62]. Studies indicate that cue-induced drug craving and impaired ability to consciously regulate ones own behavior are markers of vulnerability to relapse in SUD patients [63]. The brain fMRI correlates of these behavioral domains have been identified and found to be potentially clinically useful as markers of relapse vulnerability and response to treatment [64-66], especially when integrated with behavioral (i.e. relapse, cue-induced craving and decision-making), genetic and pharmacokinetic variables. Such an approach has been termed pharmaco-MRI (phMRI) [67-69]. The two main advantages of phMRI are increased power and additional information about mechanisms of action of the study intervention, which are not available with conventional clinical trials. Despite evidence of utility in other SUDs, phMRI has not yet been applied to POD. The primary objective of this proposal is to develop clinically useful neurobiological markers of vulnerability to relapse in POD, using a phMRI approach.

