The second clinical domain with an unmet need for objective biological markers is monitoring the treatment response. POD is epidemiologically distinct from heroin dependence by involvement of a younger patient population with a peak age of 18-25 years, lower daily doses of opioids [70] and a generally higher level of functioning. Hence, POD patients may respond differently to treatment compared to heroin dependent patients [71]. Opioid substitution therapies, such as methadone and buprenorphine, are efficacious in reducing heroin and prescription opioid (PO) use, but they are neither free from cognitive and physiological side effects [72-75] nor prevent relapse [76]. Furthermore, federal regulations limit access to agonist maintenance therapy, and daily treatment is required. Both methadone and buprenorphine because of their opioid effects are subject to illicit diversion. Because of these clinical and regulatory characteristics, antagonist treatment may be the treatment of choice in POD. Extended-release depot naltrexone (XRNT) injection is a once a month antagonist treatment that overcomes the adherence problems of the short acting oral naltrexone [77] and is not associated with the side effects and restrictions of the agonists. One preparation of XRNT (Vivitrol) has been FDA approved for the treatment opioid dependence in October 2010. At this time, there are no published reports of conventional or phMRI trials of feasibility of XRNT in POD. Hence the secondary objective of this proposal is to fill this gap by evaluating the fMRI and behavioral response to XRNT in an open-label uncontrolled feasibility trial of XRNT

in 72 POD patients.

*Study Design* **Phase\*** Not applicable

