#### Design

The proposed project will use functional magnetic resonance imaging (fMRI) and specific probes of reward and inhibition as biomarkers predicting drug use during and after treatment in 216 patients addicted to cocaine, marijuana, and prescription opioids. Participants will be scanned before, during, and after 12 weeks of active treatment specific to each of these drugs of abuse. The brain fMRI measures will be correlated with the primary clinical outcome of drug use (by urine drug screen) during the treatment and follow-up phase. An exploratory objective will examine the impact of genetic (e.g., polymorphisms modulating reward and inhibition) and epigenetic factors (e.g., history of prior trauma/ abuse) on the relapse-relevant brain measures. (Genetics are now collected under the [name] for The Genetics of Addiction Study approved by Penn IRB for the entire Treatment Research Center that has it own separate protocol (#811705) and consent).

The main strengths of the project are:

 The Treatment Research Center places a value on direct benefit to the patients participating in our research. Substance-specific pharmacological and/or psychosocial interventions are provided by certified and trained professionals. Using trained providers for the behavioral baseline treatment also reduces sources of variance extraneous to the brain predictors, giving us the best chance to determine their predictive ability.
 Inclusion of three pharmacologically distinct substances of abuse will provide robust and generalizable data on the brain predictors of relapse.

3) Using a single scanner will eliminate problems inherent to large multi-center studies that rely on more than one imaging facility, such as data incompatibility across scanner platforms.

All participants: Following successful screening, all participants will participate in the fMRI 1 and 2 sessions. Next, cocaine participants will receive a behavioral intervention (Coping with Craving), marijuana participants will be randomized (double-blind), to either baclofen or placebo and prescription opiate participants will receive naltrexone. After 2 weeks of treatment patients will participate in fMRI 3. Prior to and following each probe, craving and withdrawal will be assessed. Participants will participate in fMRI 4 at the end of Treatment. Participants will return weekly for 12 weeks during the follow up period.

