For hypotheses 2a and 2b on the rates of use after treatment, we have similar models, but fewer subjects. We expect to have 144 subjects at the start of the follow-up phase, and expect a 15% loss over the 12 weeks of follow up. With the same assumptions on correlations and rates of use as above, we have 80% power to detect odds ratios of between 1.41 and 2.04, depending on the values of the rate of use at the mean of the brain measure and of the within subjects correlations. In addition to the primary outcomes of drug use, the same ROI-based analyses can be applied to secondary outcomes of STD. And in addition to these ROI-based analyses we will also conduct whole brain regression analyses, with drug use outcome as a continuous regressor vs. the whole brain map. This approach will reveal any (novel) predictors, and the findings are data-driven (not requiring an a priori analysis). Finally, we will also explore other novel imaging analyses, including connectivity approaches (for the tasks) and classifier approaches (relapsers vs. non-relapsers, etc). These several convergent approaches will give us a high probability of identifying the strongest predictors of drug use and relapse.

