#### **Analysis Plan**

Objective 1: To determine whether differential activation in a priori brain regions of interest (ROI) to selected reward and inhibition probes can predict drug use during active treatment.

For hypothesis 1a, the two brain predictors will be the extracted signal change in the interconnected left amygdala-striatal cluster during the Brief Drug Cues task, and the extracted signal change in the bilateral ventral

striatum in the Balloon Analog Risk Task. For Hypothesis 1b, the predictors will be based on the left amygdala for the Go-NoGO contrast in the Affect-congruent Go-NoGo task, and the dorsal anterior cingulate in the Craving Inhibition task. These measures will be obtained from the fMRI 1 and fMRI 2 scans.

The four brain responses will be analyzed in a similar way. In each case, the responses will be the repeated urine screens obtained during the last ten weeks of treatment. These urine results will be binary, indicating either cocaine use, opiate use, or marijuana use, since the previous test. For each of hypotheses 1a and 1b, we will use mixed effects logistic regression (McCulloch et al, 2008) to relate variation in these responses to a measure of brain activation occurring during one of four tasks. We anticipate that using a random intercept will be sufficient to take account of within-subject correlations across the time points, although more complex covariance structures will be examined. As we are interested in assessing the separate effects of each brain region on the responses, our main analyses will consider the brain regions separately, so Hypotheses 1a and 1b will be addressed by four separate models, with the treatment urines as responses, and one brain predictor as an explanatory variable. These models will be estimated for the fMRI 1 and fMRI 3 scans.

The primary hypotheses will be addressed by the point estimates and tests of significance associated with the regression coefficients for the brain predictors in these analyses. In further analyses, we will examine the joint effects of the brain predictors for the different regions in the same model, and will use model selection based on information criteria (BIC) to determine the simplest model that provides a good fit to the data.

Objective 2: To determine whether differential activation in a priori brain ROI to selected reward and inhibition probes can predict relapse following active treatment.

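### The plan states an opioid relapse marker as a primary aim and claims generalisability across three drugs, but fits one slope common to all cohorts and so tests neither

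*Combined protocol and SAP*

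**What the plan says.** Two statements claim more than a single average association.

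- The prescription-opioid paragraphs of the Background state: "The primary objective of this proposal is to develop clinically useful neurobiological markers of vulnerability to relapse in POD". They go on to a secondary objective, an open-label feasibility evaluation of depot naltrexone "in 72 POD patients".
- The Design section lists as a strength: "Inclusion of three pharmacologically distinct substances of abuse will provide robust and generalizable data on the brain predictors of relapse".

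The operative sections treat the three cohorts as one population. The Abstract sets the goal as prediction "in patients addicted to cocaine, marijuana and prescription opiates". Objective 1 asks whether activation "can predict drug use during active treatment", and Objective 2 is "To determine whether differential activation in a priori brain ROI to selected reward and inhibition probes can predict relapse following active treatment"; neither names a cohort. The sample-size text (under Accrual) divides 0.05 by four brain regions within each objective and assigns no alpha to any cohort. For Objective 2 it states "We expect to have 144 subjects at the start of the follow-up phase" and gives 80% power for odds ratios from 1.41 to 2.04.

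The Analysis Plan defines one binary urine response that covers use of any of the three drugs. It fits four models for Objective 1, one per region, "with the treatment urines as responses, and one brain predictor as an explanatory variable". Objective 2 reuses the same type of model. The further analyses combine brain regions or explore the whole brain; none separates the cohorts.

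**The concern.** A single slope per region answers one question: is activation associated with use on average over the three cohorts? It does not say whether the association is present in opioid patients, or whether it is similar across drugs. A common slope assumes generalisability and does not examine it. A cohort main effect alone would not change this, because it adjusts for different use rates while still forcing one slope.

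Equal slopes cannot be taken for granted here. The cohorts receive different treatments (a behavioural programme; randomised baclofen or placebo; naltrexone) and view cues matched to their own drug. A positive all-cohort result could therefore come from cocaine and marijuana patients only, and the planned output would not show it. If an opioid analysis were then done to meet the Background aim, the stated 80% power would not apply to it.

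**Working it through.** **Is the planned analysis pooled?** The documents do not use the word. It follows from three facts: one response variable covering all three drugs, four models per objective, and 144 = 216 × 2/3, which is all cohorts after the stated attrition of about 33%.

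**Inputs.** Two-sided alpha 0.0125; 80% power; within-subject correlation ρ of 0.3 to 0.5; use rate p of 0.2 to 0.5 at the covariate mean; 15% loss over follow-up (all from the sample-size text); m = 12 weekly urines (Primary outcome variables). Averaged over follow-up, N = 144 × 0.925 = 133.2. The predictor is taken per 1 SD.

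**1. The plan's own range (Objective 2).**

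ln OR = √{ (z_α + z_β)² × [1 + (m − 1)ρ]/m ÷ [N p(1 − p)] }, with (2.498 + 0.842)² = 11.15.

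- p = 0.5, ρ = 0.3: √(11.15 × 0.3583 / 33.3) = 0.346, OR 1.41.
- p = 0.2, ρ = 0.5: √(11.15 × 0.5417 / 21.31) = 0.532, OR 1.70.
- p = 0.1, ρ = 0.5: √(11.15 × 0.5417 / 11.99) = 0.710, OR 2.03.

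The range 1.41 to 2.04 reproduces with the all-cohort sample. Its upper end appears to need a use rate near 0.1, outside the stated 0.2 to 0.5; values of 0.1 and 0.9 occur only in a broken sentence about Objective 1. That sentence gives no readable detectable range, so Objective 1 is not checked.

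**2. Opioid cohort alone.** 72 enrolled; with the same attrition 72 × 2/3 = 48 enter follow-up, averaging 48 × 0.925 = 44.4.

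- p = 0.5, ρ = 0.3: √(11.15 × 0.3583 / 11.1) = 0.600, OR 1.82.
- p = 0.2, ρ = 0.5: √(11.15 × 0.5417 / 7.104) = 0.922, OR 2.51.
- p = 0.1, ρ = 0.5: √(11.15 × 0.5417 / 3.996) = 1.229, OR 3.42.

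Power at an effect with 80% all-cohort power: 3.339/√3 = 1.928, and Φ(1.928 − 2.498) = 28%. Direct calculation gives 28% at 1.41 (p = 0.5) and 29% at 2.04 (p = 0.1).

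**3. Better opioid retention.** The naltrexone section reports retention above 80% at three months in earlier trials. Take 72 × 0.8 = 57.6 of a total held at 144, a share of 0.4. Then 3.339 × √0.4 = 2.112, and Φ(2.112 − 2.498) = 35%. The factor on ln OR is 1/√0.4 = 1.581, so the detectable odds ratio is 1.41^1.581 = 1.72 at p = 0.5 and 1.70^1.581 = 2.3 at p = 0.2.

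**4. All-cohort test with no opioid effect.** With equal cohorts the common slope is 2/3 of the slope in the other two: 3.339 × 2/3 = 2.226, and Φ(2.226 − 2.498) = 39%. A simulation (4,000 runs, correlated urines, logistic model with robust standard errors, not the planned mixed model) gave 34% at 1.41 (p = 0.5, ρ = 0.3) and 42% at 2.04 (p = 0.1, ρ = 0.5). By the formula, 80% is reached if the other cohorts' log odds ratio is 1.5 times larger (OR 1.41^1.5 = 1.67 or 2.04^1.5 = 2.91). Simulation at 1.67 gave 69%, so that figure is approximate.

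**The case against.** The strongest reply is that the opioid statement is component background. It names no outcome, test or alpha, and the marijuana background also uses the word proposal for its own component. Every operative section gives one set of hypotheses that single out no cohort. A reader might infer that the protocol has two rival primary hypotheses; the documents do not support that. Nor is 72 given as the sample size for the marker aim, since the text attaches it to the feasibility objective. This part of the objection stands: the text needs reconciling, and it does not set up a second formal hypothesis.

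The Background also gives a reason for a common slope, namely that drugs with different pharmacology act on the same reward circuitry. And an average association that is significant while one stratum is null is not a false positive for the average. Both are fair. But the rationale is an assumption the data could examine, and the generalisability claim depends on it.

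A reader might also infer an inflated familywise error from testing each cohort at 0.0125. The documents propose no such tests, so no error rate of that kind can be charged to the plan.

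Finally, the numbers rest on soft inputs. Opioid retention may be better than the overall figure, and cohorts may differ in information; marijuana urines, for example, stay positive for longer. This moves opioid-only power from about 28% to 35%, which is still far below 80%.

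**Conclusion.** The point holds in a limited form. The plan states an opioid marker aim in component background and claims generalisability in the Design section, but its models yield no opioid estimate and no comparison of slopes. It therefore tests neither. Only the all-cohort association is powered.

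An opioid-only analysis at 0.0125 would have about 28% power at the plan's own detectable effects (about 35% with 80% opioid retention). Its detectable odds ratio would be about 1.8 to 2.5 for use rates of 0.5 to 0.2, and about 3.4 only if the rate is near 0.1. The all-cohort test would reject about 39% of the time with no opioid effect if the other two cohorts have the stated odds ratios (34% and 42% by simulation).

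These figures are for Objective 2. They assume 72 patients in each cohort (only the opioid figure is given), equal information per cohort, a predictor scaled to 1 SD and, except in the 80% retention case, equal attrition.

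**What to change.** 1. Reconcile the opioid background with the formal Objectives. One way is to call the all-cohort coefficient primary and the opioid-only marker secondary. If the sponsor wants the opioid aim to be primary, it needs its own test, alpha and power. Name the scan to which the primary coefficient refers, because the Analysis Plan lists fMRI 1 and 2 in one place and fMRI 1 and 3 in another.
2. In the Analysis Plan, for both objectives and each of the four regions, add cohort main effects, a secondary brain-by-cohort interaction (2 df), and the three cohort-specific odds ratios with 95% confidence intervals.
3. Limit any drug-specific or generalisability claim to what those estimates show, and note that drug is confounded with treatment.
4. Beside the all-cohort range, state the opioid-only detectable odds ratios with their assumptions on use rate, correlation and retention, and say which use rate gives the stated 2.04.

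The cost is wording plus one further model per region and objective on data already collected. The downsides are an interaction test with limited power and a less favourable stated precision for the opioid component. A non-significant interaction should therefore not be read as evidence that the slopes are equal.

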#### Design

The proposed project will use functional magnetic resonance imaging (fMRI) and specific probes of reward and inhibition as biomarkers predicting drug use during and after treatment in 216 patients addicted to cocaine, marijuana, and prescription opioids. Participants will be scanned before, during, and after 12 weeks of active treatment specific to each of these drugs of abuse. The brain fMRI measures will be correlated with the primary clinical outcome of drug use (by urine drug screen) during the treatment and follow-up phase. An exploratory objective will examine the impact of genetic (e.g., polymorphisms modulating reward and inhibition) and epigenetic factors (e.g., history of prior trauma/ abuse) on the relapse-relevant brain measures. (Genetics are now collected under the [name] for The Genetics of Addiction Study approved by Penn IRB for the entire Treatment Research Center that has it own separate protocol (#811705) and consent).

The main strengths of the project are:

 The Treatment Research Center places a value on direct benefit to the patients participating in our research. Substance-specific pharmacological and/or psychosocial interventions are provided by certified and trained professionals. Using trained providers for the behavioral baseline treatment also reduces sources of variance extraneous to the brain predictors, giving us the best chance to determine their predictive ability.
 Inclusion of three pharmacologically distinct substances of abuse will provide robust and generalizable data on the brain predictors of relapse.

3) Using a single scanner will eliminate problems inherent to large multi-center studies that rely on more than one imaging facility, such as data incompatibility across scanner platforms.

All participants: Following successful screening, all participants will participate in the fMRI 1 and 2 sessions. Next, cocaine participants will receive a behavioral intervention (Coping with Craving), marijuana participants will be randomized (double-blind), to either baclofen or placebo and prescription opiate participants will receive naltrexone. After 2 weeks of treatment patients will participate in fMRI 3. Prior to and following each probe, craving and withdrawal will be assessed. Participants will participate in fMRI 4 at the end of Treatment. Participants will return weekly for 12 weeks during the follow up period.

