Study Specific Back-ground Marijuana (MJ) is the most commonly used illicit drug in the nation and in the Commonwealth. According to the 2008 National Survey on Drug Use and Health (NSDUH), an estimated 102 million Americans aged 12 or older have tried MJ at least once in their lifetime, representing 41% of the U.S. population in that age group [37]. In Pennsylvania alone, that number is greater than 1.1 million. Fifteen percent of our youth (ages 12-17) have tried MJ within the last year and 9% of them will become addicted [37]. That translates to 1 in 75 of our youth who will become dependent contributing to the mounting impact MJ dependence has on Pennsylvania. The cost of MJ dependence is great both to individuals (e.g., psychiatric

illness, cognitive deficits, and disease such as emphysema and prostate cancer) and to society (e.g., lost productivity, driving accidents and related deaths, healthcare and economic costs, law enforcement and incarceration costs) [38]. It is estimated that the Commonwealth spent \$190,445,000 just on policing, prosecuting and incarcerating marijuana offenses in 2008 alone [39].

Presently, there are no FDA approved therapies for MJ dependence however a few treatments have been investigated [40-45]. The results of these trials have been underwhelming with fewer than 50% of MJ dependent subjects remaining abstinent at 4 and 6 months following treatment [46, 47]. A greater understanding of the function-al brain substrate that is compromised in the addicted brain may lead to the development of more effective treatments, increasing the quality of life for our residents and decreasing monetary costs to society. We propose the GABA B agonist, baclofen, as an effective agent to aid in characterizing the signature of recovery. Baclofen has specific effects on the regions of the brain we hypothesize to be involved in addiction (amygdala, ventral striatum, cingulate cortex, prefrontal cortex) [48, 49] and has shown promise in treating MJ, alcohol, nicotine, cocaine and methamphetamine dependence [50] [51] [52] This proposal is specifically targeted to study, treat, and aid low income uneducated and minority MJ dependent individuals who are at greater risk of dependence. Baclofen is safe, tolerable, readily available in an inexpensive generic form, and can be offered through the public health system. Thus, the benefits to both individuals and society will be immediately realized.

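### The marijuana cohort is randomised to baclofen or placebo, but no model has an arm term, so associations with scans taken after randomisation may partly reflect assignment

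*Combined protocol and SAP*

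**What the plan says.** - **Treatment.** Under Design, "marijuana participants will be randomized (double-blind), to either baclofen or placebo". The Abstract lists "baclofen for marijuana patients and naltrexone for prescription opiate patients" and does not mention placebo. Allocation ratio and arm size are not stated.
- **Models.** The Analysis Plan addresses Hypotheses 1a and 1b by four separate mixed effects logistic models, "with the treatment urines as responses, and one brain predictor as an explanatory variable". Further work stays with brain measures: "we will examine the joint effects of the brain predictors for the different regions in the same model". Objective 2 is to use the same type of model. No term for arm or substance cohort is named.
- **Questions asked.** Objectives, outcome variables and the sample-size text under Accrual contain no baclofen-placebo question. The only treatment-response aim is for naltrexone, and it is uncontrolled.
- **What baclofen is expected to do.** The marijuana part of the background says: "Baclofen has specific effects on the regions of the brain we hypothesize to be involved in addiction". It names amygdala, ventral striatum, cingulate and prefrontal cortex, and adds that the drug is promising in marijuana dependence.
- **Scans.** For Objective 1 the Analysis Plan first takes the measures from fMRI 1 and fMRI 2, then states: "These models will be estimated for the fMRI 1 and fMRI 3 scans". Under Design, fMRI 1 and 2 precede treatment and fMRI 3 comes two weeks into it.

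**The concern.** The protocol itself asserts both links that confounding by arm requires: baclofen to the brain signal, and baclofen to drug use. If both operate, baclofen patients differ from the rest in signal and in urines, and a model without arm attributes that difference to the brain measure. Exposure at the on-treatment scan is intended, since Procedures has marijuana participants take their dose in front of staff on Scan Day 3.

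What is at stake is interpretation. The project aims at a brain-based account of relapse vulnerability, and an association produced by assignment does not support one. Patients also accept placebo and blinding without any stated analysis that uses the randomised groups.

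**Working it through.** **1. The plan's own figures.** Alpha is 0.05/4 = 0.0125 per hypothesis. For Objective 2 the plan states detectable odds ratios of 1.41 to 2.04. With log OR = (2.498 + 0.842)/√(Neff·p(1−p)), Neff = n·m/(1+(m−1)ρ), m = 12 and n = 133.2 (144 less half of the 15% loss):
- p = 0.5, ρ = 0.3: Neff = 371.7, OR = 1.41.
- p = 0.1, ρ = 0.5: Neff = 245.9, OR = 2.03.

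The range is reproduced, although its upper end needs a use rate of 0.1 (a rate of 0.2 gives 1.70). These figures concern the brain predictor. None is given for the arms.

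**2. Which models are exposed.**
- Pre-treatment scan: arm is independent of it by randomisation, so there is no bias.
- Objective 1, on-treatment scan: Objectives calls it FMRI 2, Design calls it fMRI 3, and the Analysis Plan uses both labels. Hypotheses 1a and 1b ask for a scan during treatment, so it follows randomisation whatever its number. If fMRI 2 in the Analysis Plan follows Design's numbering, that particular scan precedes treatment and is not exposed.
- Objective 2: the Analysis Plan takes fMRI 3 to be after treatment. Procedures places a fourth scan once treatment ends, and the urines come from follow-up. Exposure requires that the scan meant is the on-treatment one, or that a baclofen effect carries over.

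**3. Inputs for the size.** Total: "during and after treatment in 216 patients addicted to cocaine, marijuana, and prescription opioids". Only the opioid cohort has a stated size, "in 72 POD patients". I assume 216/3 = 72 in marijuana and 1:1 allocation, so baclofen patients are one sixth of the sample. Objective 1 has 20 urines (two a week for ten weeks). Effect sizes are not in the documents. I assume that baclofen lowers the signal by δ SD and multiplies the odds of a positive urine by OR_b, with no link between brain and use within arm.

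**4. Approximate induced slope, pooled model without cohort or arm.** With v = (1/6)(5/6) = 0.139, the log odds per SD of signal is |δ|·|ln OR_b|·v/√(1+δ²v).
- δ = 0.5, OR_b = 0.5: 0.5 × 0.693 × 0.139/1.017 = 0.047, OR about 1.05.
- δ = 0.8, OR_b = 0.33: 0.8 × 1.109 × 0.139/1.044 = 0.118, OR about 1.13.
- δ = 0 (pre-treatment scan): zero.

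**5. Simulated null rejection at two-sided 0.0125.**

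Simulation A: 156 patients (52 per cohort, between the 173 left after 20% attrition and the 144 left after 33%), 20 urines, latent correlation 0.4, logistic regression with subject-level robust standard errors, 4,000 runs.

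| Assumed baclofen effect | As written | With arm and cohort | Mean spurious OR, as written |
|---|---|---|---|
| None | 0.014 | 0.015 | 1.00 |
| 0.5 SD, OR 0.5 | 0.024 | 0.014 | 1.04 |
| 0.8 SD, OR 0.33 | 0.064 | 0.0135 | 1.09 |

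These odds ratios are averaged over patients, so they lie below the subject-specific values in step 4.

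Simulation B: 58 per cohort, mean use 0.4, random-intercept SD 1.5, regression of each patient's proportion of positive urines, 6,000 runs. From 0.5 SD with OR 0.5 to 0.8 SD with OR 0.3, rejection is:
- as written: 0.021 to 0.059 (0.020 to 0.055 in a repeat);
- cohort terms only: 0.017 to 0.030;
- cohort and arm: 0.012 to 0.016 (0.013 to 0.014 with arm in the repeat).

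A cohort term alone does not remove the problem at the larger effect. Both simulations stand in for the planned mixed model.

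**6. What the arm comparison could detect.** At two-sided 0.05, 80% power, an assumed 36 per arm and 20 urines, OR = exp(−2.802·√(2/(Neff·p(1−p)))).
- p = 0.5, ρ = 0.3: Neff = 107.5, OR = 0.47.
- p = 0.2, ρ = 0.5: Neff = 68.6, OR = 0.30.

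**The case against.** The strongest reply is that the objectives concern prediction, and an unadjusted association still predicts. Every hypothesis also uses the pre-treatment scan, which arm cannot bias. Both statements are right. The first does not rescue the reading of the coefficient as a brain vulnerability separate from treatment.

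The effect sizes are assumed and may be generous. The protocol notes that marijuana urines can stay positive from earlier use, which would dilute an arm effect on urines. The spurious odds ratios of 1.04 to 1.09 are small beside the smallest stated detectable value, 1.41 for Objective 2. The background gives no direction for baclofen's action on each region, and Hypotheses 1a and 1b predict opposite signs. An arm effect could therefore mimic, mask or oppose a hypothesis, and the two-sided rejection rates count all of these. All of this stands, and it limits the claim to a possible distortion of unknown size.

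A reader might infer that the randomised comparison is lost. It is only unplanned: nothing in the documents prevents an analysis by arm. A reader might also quote the marijuana cohort alone, where simulation A gives 0.024 and 0.072 without arm. The plan contains no marijuana-only test, and that model already rejects at 0.020 with no baclofen effect.

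**Conclusion.** The point holds for models that use a scan taken after randomisation: clearly the on-treatment scan in Objective 1, and Objective 2 only under the conditions in step 2. There, part of any association between brain signal and use may reflect assignment to baclofen or placebo.

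Under the assumed effects, null rejection at nominal 0.0125 is about 0.02 to 0.06 in the pooled model as written and about 0.013 with arm added. This rests on equal cohorts, 1:1 allocation, the assumed effect sizes and stand-in models.

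A reader might infer a five-fold error rate (0.06/0.0125 = 4.8) or bias across all the objectives. The documents support neither. The multiple comes from the larger assumed effect, the smaller gives 0.02/0.0125 = 1.6, and the pre-treatment models are untouched. Adding arm is a free improvement; its absence does not invalidate the plan.

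**What to change.** - In the Analysis Plan, for both objectives, add randomised arm (baclofen versus placebo, coded within marijuana) and substance cohort as fixed effects in every model that uses a post-randomisation scan. In models on the pre-treatment scan the arm term is harmless but not needed against bias.
- Report baclofen against placebo on the treatment urines and on the on-treatment regional signal, by arm as randomised, and label it exploratory. It adds a question to the stated objectives and, at the assumed size, could detect only large effects. State the allocation ratio and arm sizes.
- Reconcile the marijuana treatment described in the Abstract with that in Design. Reconcile the scan numbering across Objectives, Design, Procedures and the Analysis Plan, so that each model names its scan by timing.

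The cost is wording, one degree of freedom for arm and two for the three cohorts. Assignment arises from the randomisation itself, so no new data are needed.
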